#### **Aim4:**

We will use chi-square tests and/or t-tests as appropriate to compare patient satisfaction between navigated and non-navigated patients.

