### **III. SUBJECT SELECTION**

According to internal MGH data from 2012, 1480 patients aged 55-79 years at MGH CHCs were current smokers. Of these patients, 204 had a chest CT scan in the prior 18-months and/or had a diagnosis of lung cancer. Because of new Medicare guidelines we will only include patients that are aged 55-77 years and additionally exclude patients that providers deem ineligible for lung cancer screening. We estimate the total number of patients eligible for our interventions to be around 1200. Our experience in prior PN colorectal cancer screening interventions is that one full-time navigator assigned 400 patients will be able to reach/work with 300 patients over a 9-month period. Since our navigator will also follow-up abnormal CT results, our study will last one year. Eligible patients will be identified, randomized, and an electronic list of patients will be downloaded into an existing TopCare navigator data base. The navigators will use this system to track patients and interventions. Patients randomized to the interventions group will be recruited by navigators during their visits to the health center or over the phone. Since the navigator program is already standard of care at MGH, its expansion to include lung screening is considered part of usual care.

For Specific Aim 5, primary care physicians (PCPs) and nurse practitioners (NPs) from the community health centers with the PN program will be asked to complete a survey following the study period. There are approximately 81 PCPs and NPs who will be asked to complete the survey.

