As a part of lung screening, the PN will assess the patient's interest in quitting smoking. If the patient is interested in quitting, the PN will offer and help to connect the smoker to existing cessation resources in the community and CHCs and provide follow-up contacts to monitor adherence to treatments. The PN will direct smokers to the 5-call proactive telephone smoking cessation counseling provided free by the MA Quitline. The PN will use a QuitWorks fax-referral system to make the Quitline referral; by doing so, the smoker is eligible for two weeks of free nicotine patch or gum as well. The PN will also explain that pharmacologic treatment doubles quit rates when added to behavioral counseling, describe the available FDA-approved smoking cessation medications (nicotine replacement products, bupropion, and varenicline), and refer to the PCP for a recommendation and prescription. The PN will monitor patient progress by contacting the patient weekly for up to six weeks, followed by monthly follow-up until the end of the study. If a patient declines smoking cessation assistance, the PN will continue to inquire every three months if the patient has changed his/her mind about cessation and/or LDCT screening. Navigators will record information on every patient they contact and note all the interventions that were attempted.

For the patient satisfaction surveys in Specific Aim 4, patients will be contacted by telephone and asked to participate if they received PN services as part of the lung screening PN program and have contact with the navigator. We will also randomly select patients from the delayed intervention/control group to complete a satisfaction survey.

For the PCP and nurse practitioner (NP) surveys in Specific Aim 5, PCPs and NPs will be provided a paper survey at regular practice meetings by the PI of this study and asked to complete the survey. Providers that do not attend the practice meeting will receive the request to fill out the survey via interoffice mail or email.

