#### **V.6. Patient Satisfaction Surveys (Specific Aim 4)**

We plan to collect quantitative data about patient satisfaction with the navigators in Lung screening patient navigation (PN) program. We will ask patients who have been randomized to PN early intervention arm to complete two validated surveys: "Satisfaction with Interpersonal Relationships with Navigator (PSN-I)" and "Satisfaction with Logistical Aspects of Navigation (PSN-L)". We will also ask both the PN early intervention group and the delayed intervention group to complete the Short-form Patient Satisfaction Questionnaire (PSQ-18). These surveys will provide information about patient satisfaction with the PN program and information about the impact of the PN program on overall patient satisfaction with medical care.

Patients will be contacted by telephone and asked to participate if they received PN services as part of the Lung screening PN program and had contact with navigator. Those interested in participation may then complete the surveys over the telephone or they may elect to complete the surveys in person and will be met by an interviewer at their next MGH clinic appointment. Patient interviews will last approximately 20 minutes in duration (see attached surveys and interview guide). Bilingual research assistants or trained interpreters will be available to conduct surveys if patients are not native English speakers. Exclusion and inclusion criteria are the same as Specific Aim 2.

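### Aim 4 compares satisfaction between intervention patients filtered on navigator contact after randomisation and a random draw of all controls, so the difference cannot be read, free of selection bias, as the programme's impact

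*Combined protocol and SAP*

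**What the plan says.** Section VI.3, Aim 4, gives the whole analysis in one sentence: by chi-square test or t-test, the plan will "compare patient satisfaction between navigated and non-navigated patients". It mentions no covariates, no handling of survey non-response and no comparison by assigned arm.

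Section IV sets who is surveyed. On the navigation side, patients are "asked to participate if they received PN services as part of the lung screening PN program and have contact with the navigator", and section V.6 repeats the condition. On the control side: "We will also randomly select patients from the delayed intervention/control group to complete a satisfaction survey". No matching condition is placed on controls.

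Section V.6 reserves PSN-I and PSN-L, which concern the navigator, for the early intervention arm. PSQ-18, which concerns medical care in general, is the instrument common to both arms: "We will also ask both the PN early intervention group and the delayed intervention group to complete the Short-form Patient Satisfaction Questionnaire (PSQ-18". The same section says the surveys will yield "information about the impact of the PN program on overall patient satisfaction with medical care".

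**The concern.** PSQ-18 can be answered by any patient in either arm, so a comparison protected by randomisation is available. The plan does not use it. Having contact with the navigator and receiving services are events after randomisation that can occur only in the intervention arm. Patients who answer calls, keep appointments and accept help may rate their care differently from those who do not, whatever the navigator does. Removing the second kind of patient from one side only leaves two groups that need not be comparable even if the programme has no effect.

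The plan recognises this problem in Aim 2. There, contacted intervention patients against all controls is a secondary, as-treated outcome (VI.2, item 1), behind an intention-to-treat primary outcome (VI.1). Aim 4 makes the same kind of contrast its only between-group comparison, without the label, and attaches the word impact to it. Section VIII says the knowledge gained will be used to modify navigation programmes, so the reading has practical consequences.

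**Working it through.** **No figure to reproduce.** The documents give no sample size, SD, target difference, power or response rate for Aim 4. What follows only gauges how large the bias could be.

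**Inputs**
- Share reached, c. Section III says "one full-time navigator assigned 400 patients will be able to reach/work with 300 patients over a 9-month period", so c = 300/400 = 0.75. Section VI.4 says that a full-time navigator with two part-time interpreters/navigators can reach about 400, so c is near 1.
- Correlation ρ between satisfaction and a latent (continuous, normal) reachability score: 0.1 to 0.3, assumed.
- Respondents per group: 100 and 300, assumed. Under section III, 300 is the ceiling on the navigated side.

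**Step 1: shift from the contact filter alone, with no programme effect.** If the most reachable share c is contacted, their mean reachability is φ(z)/c, where z cuts off the lowest 1 − c. At c = 0.75, z = −0.674 and φ(z) = 0.318, so the mean is 0.318/0.75 = 0.424. The shift in mean satisfaction is ρ × 0.424:
- ρ = 0.1: 0.042 SD
- ρ = 0.3: 0.127 SD

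At c = 1 the shift is zero.

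**Step 2: cross-check with another parameterisation.** If reachable and unreachable patients differ by d SD, the contacted mean exceeds the whole-arm mean by (1 − c) × d. At c = 0.75 this is 0.05, 0.075 and 0.125 SD for d = 0.2, 0.3 and 0.5 (assumed), which is the same order. The meaning of ρ matters. As a correlation with the yes/no event of being reached, 0.1 to 0.3 would give ρ × √(0.25/0.75) = 0.06 to 0.17 SD.

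**Step 3: false-positive rate of a two-sided 5% test.** The standard error of the difference, in SD units, is √(2/n).

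| n per group | SE | shift 0.042 | shift 0.127 |
|---|---|---|---|
| 100 | 0.141 | 6% | 15% |
| 300 | 0.082 | 8% | 34% |

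**Step 4: let the survey filter both groups.** Steps 1 to 3 treat control respondents as a random sample of their arm, but a control must also be reached and agree to answer. Assume survey reach of 50 to 60%, a correlation of 0.5 to 0.9 between navigator and survey reachability, and satisfaction tied equally to both scores with ρ = 0.1 to 0.3. By simulation, the remaining shift is 0.00 to 0.06 SD, and the false-positive rate is 5 to 7% at n = 100 and 5 to 11% at n = 300. If satisfaction follows navigator reachability alone, the top of the shift range becomes 0.07 SD. Steps 1 to 3 are therefore close to an upper bound for the contact filter under their own assumptions.

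**The case against.** **Both arms are asked.** The V.6 sentence on PSQ-18 names both groups and, on its own, could mean a survey by arm. The next paragraph of V.6, section IV and the navigated/non-navigated wording of VI.3 all point to contacted patients only. At the least, the passages need reconciling.

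**Controls must be reached too.** This stands, and it shrinks the bias (Step 4). It does not remove it: navigation respondents pass navigator contact and receipt of services and then the survey, while controls pass only the survey. If receiving services means more than the first call, screening eligibility and interest become further one-sided filters.

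**Nearly everyone may be reached.** Under VI.4 the reach bias is about zero. But III says 300 of 400, and VI.3 plans to report the percentage reached, so complete contact is not assured.

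**Aim 4 is ancillary.** It carries no hypothesis or power statement, and its stated purpose is satisfaction with the navigators. PSN-I and PSN-L serve that purpose and are unaffected. This bears on how serious the point is. It does not answer a between-group test tied to impact.

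**Stronger readings the documents do not support.** A reader might infer that the bias must favour navigation. That assumes reachable patients are more satisfied, which no passage shows, and section VII notes that the contact may distress some patients. A reader might also take the 34% in Step 3 as the expected false-positive rate. It needs all 300 reached patients to complete an interview of about 20 minutes, the top of an assumed correlation range, and no allowance for control non-response.

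**Conclusion.** The point stands as a flaw of design and interpretation. A filter applied after randomisation to one side only, followed by unadjusted tests, gives up the protection of randomisation, and nothing else in the plan restores it.

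The size and direction of the bias cannot be derived from the documents. From the contact filter it is about zero if nearly all 400 are reached. At 75% reached it is at most roughly 0.04 to 0.13 SD for an assumed latent correlation of 0.1 to 0.3, and smaller, about 0.00 to 0.06 SD, under the assumed survey filter of Step 4. Any extra selection through receipt of services is not in these figures.

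A reader might infer that the comparison says nothing about the programme. That goes too far: V.6 promises only information about impact, and the contrast remains usable as a description. What it cannot support is an unbiased reading as programme effect. The primary outcome and the other Aim 2 results are not touched.

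**What to change.** 1. For PSQ-18, draw respondents from all patients assigned to the intervention arm, contacted or not, under the same sampling and call rules as controls. Compare by assigned arm, and report survey response by arm.
2. If contacted patients are also compared with controls, label that comparison descriptive and as-treated, as Aim 2 does.
3. Keep PSN-I and PSN-L among contacted patients, with no control comparison.
4. Reconcile the sampling statements in IV and V.6 with the Aim 4 sentence in VI.3, and tie the impact statement to the by-arm comparison.

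**Cost.** Uncontacted respondents dilute the difference: if navigation changes satisfaction only in the contacted, 75% contact among respondents gives 0.75 of their effect. That is the effect of offering the programme. A whole-arm sample also yields fewer PSN respondents. With equal response, n interviews give about 0.75n, so keeping 100 PSN respondents takes about 100/0.75 = 133 intervention-arm interviews, or a separate approach to contacted patients for those two surveys. Patients the navigator could not reach may not answer the survey either, so the change reduces the bias but may not remove it.

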### **VI.4. Sample Size Calculations**

We hypothesize that the navigator program will increase lung screening in the intervention group by at least 5%. With a total sample size of 1276 smokers, 400 randomized to the intervention group, and an alpha level of 0.05, we will have 88% power to detect a 5% difference. From our prior experience, a full time navigator with the assistance of two part-time interpreters/navigators can reach about 400 patients over nine months. Since our intervention includes follow-up of abnormal results, our study will last 1-year.

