### **IV. SUBJECT ENROLLMENT**

For this study, we will use a newly developed TopCare smoking and lung screening registry. The registry uses the data from patient's EMR regarding the smoking history and imaging (most recent chest CT) and it is daily

updated. We will choose the current smokers age 55-77 from the registry who did not have chest CT in the last year receiving care at MGH health centers. We will e-mail primary care providers a list of their patients and ask them to notify us in a week if they do not want us to contact a patient and to provide a reason why they believe patient is not eligible for lung screening. Patients meeting eligibility criteria for the study according to the criteria above will be identified and randomly assigned to navigation or control group. An electronic list of patients assigned to the intervention group will be downloaded into an existing TopCare navigator data base. The navigators will use this system to track patients and record interventions. Patients randomized to the intervention group will be recruited by navigators during their visits to the health center or over the phone. Since the navigator program is already standard of care at MGH, its expansion to include lung screening is considered part of usual care.

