#### **V.4. Randomized Clinical Trial (Specific Aim 2)**

To test our hypothesis we will randomize eligible patients receiving care at CHCs to one of two study groups:

Early intervention	Usual care/delayed intervention
400 patients will receive 1:1 PN to obtain lung screening and follow-up of abnormal results, as well as smoking cessation guidance	800 patients will receive usual care during the 1-year study period. After the study period they will be offered 1:1 PN to obtain lung screening and follow-up of abnormal results as well as smoking cessation guidance

Eligibility criteria:

1. Inclusion criteria: adult patients aged 55-77 years who are current cigarette smokers (according to an algorithm using EMR data), and receive care at one of the five MGH CHCs.
2. Exclusion criteria: 1) patients who have previously received a diagnosis of lung cancer per EMR, 2) have undergone a chest CT within 18 months before enrollment, 3) are subsequently identified as having died prior to the study intervention 4) deemed by their primary care provider as not eligible for lung screening

Patients will be identified using existing electronic systems developed by the MGH Primary Care Operations Improvement (PCOI) program (Protocol # 2004P002796).

Using a newly developed TopCare smoking and lung screening registry, we will identify smokers receiving care at MGH health centers who could be eligible for lung screening. We will e-mail primary care providers a list of their patients and ask them to notify us in a week if they do not want us to contact a patient and to provide a reason why they believe patient is not eligible for lung screening. The eligible patients will then be randomly allocated to the intervention or usual care groups. Patients randomly assigned to the intervention group will be eligible for PN, while patients randomly assigned to the control will receive usual care and be eligible for navigation after the one year period.

Patient navigator intervention:

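### VI.4 states power for 1276 smokers and no control rate, but V.4 randomises 400 + 800; the chest-CT look-back and the name of the primary outcome also differ between sections

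*Combined protocol and SAP*

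**What the plan says.** **Size.** VI.4 hypothesises that the "navigator program will increase lung screening in the intervention group by at least 5"% and continues: "With a total sample size of 1276 smokers, 400 randomized to the intervention group, and an alpha level of 0.05, we will have 88"% power for a 5% difference. It gives no control-group rate and does not say whether the test is one- or two-sided.

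Section III shows where the count comes from: "1480 patients aged 55-79 years at MGH CHCs were current smokers", of whom "204 had a chest CT scan in the prior 18-months and/or had a diagnosis of lung cancer". It then narrows the age range to 55-77 and will "additionally exclude patients that providers deem ineligible for lung cancer screening". Its conclusion is: "We estimate the total number of patients eligible for our interventions to be around 1200". The design table in V.4 assigns 400 patients to early intervention, and "800 patients will receive usual care during the 1-year study period".

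**Look-back.** Section IV takes current smokers aged 55-77 "from the registry who did not have chest CT in the last year", and randomises those who meet the criteria set out above that point. The exclusion criteria in V.4 remove anyone with a chest CT in the 18 months before enrolment.

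**Outcome.** V.1 and VI.1 define the primary outcome as at least one chest CT during the one-year study period. VI.3 describes the Aim 2 comparisons, including the intention-to-treat one, as differences in lung screening rates, and VI.4 powers an increase in lung screening. VI.2 item 3 distinguishes LDCT from diagnostic chest CT.

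**The concern.** The power statement should let a reader check the trial that will be run. Here the total belongs to a wider pool than the one randomised. The figure that most affects power, the control rate, is absent, so the 88% cannot be verified from the plan.

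The two look-backs affect who enters the trial. A patient last scanned 15 months ago is eligible under Section IV and excluded under V.4.

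The outcome wording affects what the trial can report. Any chest CT includes scans done for diagnostic reasons. Aim 2 is about improving screening rates, yet no outcome in VI.1 or VI.2 clearly isolates screening LDCT in all randomised patients by arm.

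**Working it through.** **Inputs from the documents.** 1480, 204 and about 1200 (Section III); 400 and 800 (V.4); 1276, 400, alpha 0.05, 88% and a 5% difference, read as percentage points (VI.4); chi-square test (VI.3).

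**Inputs assumed.** The control rate, because none is stated, and a two-sided test.

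**Step 1: origin of the total.** 1480 − 204 = 1276. With 400 in the intervention group, VI.4 implies 1276 − 400 = 876 controls. V.4 has 400 + 800 = 1200. The gap is 76 patients, or 76/1276 = 6.0%.

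**Step 2: the stated 88%.** For a pooled-variance two-proportion test with n1 intervention and n0 control patients and rates p1 = p0 + 0.05 and p0:

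- p̄ = (n1·p1 + n0·p0)/(n1 + n0)
- SE0 = √[p̄(1 − p̄)(1/n1 + 1/n0)]
- SE1 = √[p1(1 − p1)/n1 + p0(1 − p0)/n0]
- power = Φ[(0.05 − 1.96·SE0)/SE1]

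Solving for the p0 that gives 88% at 400 vs 876 returns 5.35%. So the figure is attainable, but the implied rate depends on the method: 4.2% with unpooled variance, 4.8% with a continuity correction, and 7.3% if the pooled test is one-sided. The plan does not say which was used.

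**Step 3: effect of the size mismatch.** At an assumed 5% vs 10%:

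- 400 vs 876: p̄ = 83.8/1276 = 0.0657; SE0 = 0.01495; SE1 = 0.01671; (0.05 − 0.02930)/0.01671 = 1.239; power 89.2%.
- 400 vs 800: p̄ = 80/1200 = 0.0667; SE0 = 0.01527; SE1 = 0.01686; (0.05 − 0.02994)/0.01686 = 1.190; power 88.3%.

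The loss is 0.9 point here and at most 1.4 points at any control rate scanned. At the back-solved 5.35%, power falls from 88.0% to 87.0%.

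**Step 4: effect of the control rate.** Gain of 5 points, two-sided pooled test, all control rates assumed:

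| Control rate | 400 vs 876 | 400 vs 800 |
|---|---|---|
| 3% | 95.7% | 95.2% |
| 5% | 89.2% | 88.3% |
| 7% | 82.1% | 80.9% |
| 9% | 75.4% | 74.0% |

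At 400 vs 800, power is at least 88% up to a control rate of 5.1% and at least 80% up to 7.2%. Between 5% and 9% it falls by about 14 points, against about 1 point for the size mismatch.

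**Step 5: look-back.** VI.4 states no look-back. The 18 months enters only through the 204 and agrees with V.4, so the conflict lies between Section IV and V.4. The number of patients affected cannot be calculated. The documents do not say how many of the 204 were last scanned 12 to 18 months earlier, or how many were counted only for a lung cancer diagnosis.

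**Step 6: outcome wording.** VI.3 names two overall comparisons, intention-to-treat and as-treated. VI.1 and VI.2 item 1 define outcomes for both, in terms of chest CT. Aim 3 follows the same pattern: its outcome measure is a chest CT and its analysis compares lung screening rates. V.1 also describes the subgroup item as the primary outcome, stratified. The natural reading is that lung screening is shorthand for any chest CT. On that reading, the only item that names CT screening by arm (VI.2 item 2) is the stratified primary outcome, and the process measure in item 7 covers only intervention patients who were reached. Neither is an overall comparison of screening LDCT by randomised arm.

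**The case against.** The strongest defence is that little of this changes the trial. At the V.4 sizes, 5% vs 10% still gives 88.3%, and Section III openly explains the step down to about 1200, so 1276 is simply a figure that was not updated. Section IV describes a registry pull, and one year is the looser screen, so the V.4 exclusion could be applied afterwards. These points stand as to size. They do not remove the inconsistencies: the total in VI.4 is still not the design's, and Section IV refers back to its own criteria when it randomises.

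A reader might infer more than the documents support:

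- *That the 88% is wrong or the trial underpowered.* This is not shown. A control rate near 5% reproduces the figure, and Section II says that LDCT was not widely used at the hospital. That statement suggests a low screening rate but does not cover diagnostic scans.
- *That the control rate must be about 9%.* 204/1480 = 13.8%, and 13.8% × 12/18 is about 9% a year. But the 204 include lung cancer cases, come from ages 55-79, and are the people whom V.4 keeps out. This is not a control rate for the enrolled patients. It gives no support for 5% either.
- *That VI.3 plans an LDCT comparison missing from VI.1 and VI.2, or that the 5 points refer to LDCT and diagnostic scans dilute them.* The Aim 3 usage and the match between VI.3 and the listed outcomes favour the shorthand reading, and the documents give no diagnostic-scan rate from which to size a dilution.

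Adding an LDCT outcome is therefore a way to serve Aim 2 better, not the repair of a contradiction.

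**Conclusion.** The concern holds in a limited form. The total in VI.4 is not the total randomised in V.4; that alone costs about 1 point of power and is minor. The more important gap is that the 88% rests on an unstated control rate. Under a two-sided pooled test at 400 vs 800, it holds for a 5-point gain in any chest CT only up to a control rate of about 5%. A one-sided test would move that limit to 6.9%, and the plan does not state sidedness.

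The look-back conflict is a separate eligibility point, of unknown size.

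The outcome wording is probably shorthand. The primary comparison remains valid because randomisation balances diagnostic scans between arms. What is lacking is a clear overall result for screening itself. None of this threatens the design, and all of it can be corrected cheaply.

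**What to change.** 1. **VI.4.** Restate for 400 intervention and 800 control patients, two-sided chi-square test, alpha 0.05, and a gain of 5 percentage points in any chest CT. Give the assumed control rate and its source, and show power over a range: 95%, 88%, 81% and 74% at control rates of 3%, 5%, 7% and 9%. The source should be data on patients like those enrolled; 5% should not be adopted merely because it returns 88%. If the sourced rate is above about 5%, restate the 88%.
2. **Outcome.** Use *any chest CT* for the primary outcome in V.1, VI.1, VI.3 and VI.4. Record scan type (screening or diagnostic) in the blinded chart review already planned in VI.2. Add a secondary outcome: the percentage of all randomised patients with at least one screening LDCT in the study year, by randomised arm, intention-to-treat.
3. **Look-back.** Reconcile Section IV with V.4, and state which look-back the eligible count uses.

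**Cost.** Wording changes in five or six sections, one more secondary comparison, and one extra field in the chart review. The field would cover about 80 records at an assumed 5% vs 10% (800 × 0.05 + 400 × 0.10), or 128 at 9% vs 14% (800 × 0.09 + 400 × 0.14). There are no extra patients and no change to the primary outcome or its test.
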